The main outcomes commonly evaluated in oral surgery literature have been (1) pain, (2) swelling, (3) trismus and (4) bony healing. This is relevant to the evaluation of any potential outcome improvement from utilising knotless sutures. Our intended study will draw on this body of knowledge, however we will focus on assessment of swelling, pain and patient perceived irritation at the procedural site.

Visual analogue scales (VAS) have been used to measure patient-perceived postoperative pain (Berge, 1988, 1989). The use of the VAS as a pain measure is well documented and robust (Huskisson, 1974; Scott & Huskisson, 1976). A 100mm VAS was used by Lau et al (2020; in press) to assess third molar surgery outcomes, with 0 representing no pain and the 100mm mark representing the worst perceived pain possible. With respect to irritation at the procedural sites, Rodanant et al., (2016) used the VAS to assess irritation following closure using silk sutures. Bello et al. (2011) used a manual tape measure method to compare pre- and postoperative swelling. They utilised fixed points of reference on a patient's face and recorded the sum of these measurements. A limitation of this method is soft tissue compression during measurement, which would lead to systematic error. Non-contact measurement methods such as stereophotography and 3-dimensional (3D) scanning have been used in the literature to circumvent these limitations in measurement of facial swelling (Lau, 2020; in press). However, this requires specialised imaging capabilities that may not necessarily be readily available across study sites.

Review intervals in studies, following third molar surgery, varies depending on the variable being evaluated. Some previous studies reviewed patients at days 1 and 7 following third molar surgery with no further recorded follow-up within the study (Brüllmann et al., 2014; Kumar et al., 2015; Matsuda et al., 2016; Pasqualini et al., 2005; Rana et al., 2011). Other studies, particularly interventional studies, evaluating the usage of platelet-rich fibrin (PRF), had longer follow-up periods of up to 3 months (Kumar et al., 2015; Marenzi et al., 2015). On the other hand, studies that looked at flap design or topical corticosteroids, generally reviewed partcipants for the last time 10 days or less following surgery (Alcântara et al., 2014; Dubois et al., 1982; Hu et al., 2017; Matsuda et al., 2016; Pasqualini et al., 2005).

Problem statement

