Conventional wound closure in third molar surgery involves simple interrupted multifilament sutures. The knot takes time to tie, causes irritation, stress concentration, and is an area of focal weakness in the suture. Clinically, multifilament sutures pose an issue due to capillary action, which draws bacteria and saliva along the material, through the mucosa, and accumulates debris and plaque, which increases inflammation. Since monofilament knotless sutures do not have the same capillary action that multifilament sutures do, they eliminate issues associated with this. The use of knotless sutures in other areas of surgery is supported by a strong body of evidence, however, intraoral usage, particularly in third molar surgery has yet to be explored.

Aims of study

To evaluate the benefits of knotless sutures over conventional sutures for wound closure in third molar surgery.

Objectives

Primary objectives

- To determine if there is any difference in wound closure time between conventional and knotless sutures
- To determine if there is any improvement in post-operative outcomes from using knotless sutures in third molar surgery, measured as:
 - Pain (VAS)
 - Swelling (Facial measurements)
 - Tissue irritation (VAS)

Secondary objectives

- To determine if the savings obtained in operating time reduction justifies the increased material cost of knotless sutures.
 - Is there an impact on overall treatment cost provision?
- Patient's impression on healing of the surgical third molar extraction site and post-operative comfort between the two materials.
- To determine if patients perceive an improvement in QoL following third molar surgery.

Implications

Potential benefits

The current body of literature is built upon clinical studies carried out in other areas of surgery. There is no convincing evidence at present to support or refute the use of knotless sutures in third molar surgery, hence, further clinical investigation would help us evaluate the validity of this particular application.

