- 1. Eligible patients will be invited to participate and will be provided with a copy of the participant information sheet if they express interest. The initial appointment will involve a consultation with the clinician/primary investigator. If the patient provides informed consent to participate, they will then complete the pre-operative questionnaire. This questionnaire contains the Oral Health Impact Profile, OHIP-14 (Slade, 1997), Locker's Global Oral Health Item (Thomson et al., 2012), and the Dental Anxiety Scale (Corah, 1969).
- 2. Patients will be assigned a study participant number which will be used during data collection. This will be recorded separately from their clinical records. According to the applicable institutional protocol, the intervention site, material and batch number will be recorded in the patient's clinical record.
- 3. The type of third molar impaction according to the Winter's classification (mesio-angular, disto-angular, vertical, horizontal, transverse bucco-lingual, inverted) will be recorded for each participant. Clinically and radiographically similar impaction patterns are crucial in a split-mouth design.
- 4. Prior to the procedure, the patient will:
 - i. Complete a VAS score on pre-operative pain and irritation;
 - ii. Have a triplicate of baseline measurements to later aid in assessing facial swelling will be recorded.
 - iii. Have their height and weight taken.

The removal of the bilateral similarly impacted third molars will then commence under IV sedation.

5. The time taken for removal of the mandibular third molar from each side will be recorded, starting from the time of the initial incision to the completion of tooth removal. Both sites will be irrigated and inspected to remove and fine debris in the surgical site, ensure no remnants remain and there is no inadvertent damage to adjacent structures. The time taken for wound closure will also be recorded, starting from the time of the first bite of the soft tissue, to the time the sutures have been placed and the wound edges satisfactorily approximated.

- i. Prior to the procedure, the side receiving the intervention will be drawn.
- ii. This will be drawn at random, with the nurse and the clinician unaware of which side the intervention is assigned to until the envelope is opened.

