- 6. Participants will be asked to rate the pain and irritation experience at each side every 6 hours while awake for the first 48 hours. A non-graduated 100mm VAS, in the patient's post-operative diary will be included, for every waking 6 hour interval.
 - i. They will additionally record under the respective pages:
 - i. The time between the end of the procedure (will be written down into the booklet at the conclusion of the procedure) and the first use of rescue medication
 - ii. The amount of rescue analgesia consumed each day
 - iii. Any adverse events experienced post-operatively (e.g. vomiting, nausea, headaches, uncontrolled pain and swelling from the site)
- 7. Participants will be asked to attend a post-operative review with the primary investigator at 48h following their procedure, and again at 7 days.
 - i. A repeat triplicate of facial swelling measurements will be taken at each of these appointments.
 - ii. A post-operative questionnaire will be completed at each appointment. This contains items relating to post-operative pain, irritation at the sites, whether they needed to be reviewed in a community-based practice or at the institution in the intervening period, whether intervention was required, compliance with the prescribed pain relief, requirement for rescue analgesia, OHIP-14, Locker's global oral health measure. Additionally, the patient's perception of which side they felt was healing better will be recorded.

Measurement of facial swelling

Facial swelling will be determined by tape measurements between the tragus and soft tissue pogonion (A), tragus and lateral corner of the mouth (B), lateral corner of the eye and the angle of the mandible (C). Facial measurements will be calculated as: (A

+B+C)/3, and facial swelling (%) will be calculated as: [(postoperative measurement – preoperative measurement] × 100% (Baqain et al., 2012).

- 1. These measurements will be taken prior to commencement on the day of the procedure;
- 2. 48h post-operatively;
- 3. 7 days post-operatively.

Data entry

Data will be entered into a Microsoft Excel spreadsheet, recording the triplicate of facial measurements, the nature of impaction involved, the time taken to close the surgical site, the intervention side/site and scores from the operative questionnaires. The data will be checked for errors prior to de-identification and data analysis.

Statistical considerations and data analysis

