Sample size. Power analysis yielded a sample size of 63 participants based on a paired sample t-test analysis with alpha of 0.01, power of 0.9, and a moderate effect size (Cohen's d = 0.5). Previous research supports that moderate to large effect sizes can be expected for our key outcome, closure time (Durand, 2017; Zhu et al., 2017). Furthermore, a simulation study on the sample considerations of split mouth designs also indicated that a sample size of approximately 60 participants would be appropriate. 70 participants will be recruited to account for possible drop-out and data loss from participant protocol deviation.

Statistical approach. Statistical analyses will be conducted using the statistical programming language R. Our outcome variables, closure time, inflammation, and pain, will be modelled using separate mixed models Analyses of Variance (ANOVA) with suture type as a within-subjects variable and age, sex, ethnicity, smoking status, previous pericoronitis and dental anxiety score as between-subjects variables. In the case of inflammation, irritation and pain, we will use a repeated measures design to account for multiple follow-ups. A post-hoc polynomial comparison of follow-up outcomes by suture type will also be used to determine whether the trajectory of healing differed significantly between suture types. In all cases, we will use an alpha

of 0.01, more stringent than the traditional 0.05. Using a lower alpha allows us to be more certain of our findings and also implicitly controls for the multiple comparisons we are making across different outcome variables.

Bias and confounding

Bias

The patient is blinded to which side receives the intervention to minimise reporting bias. Handedness will be controlled for by allocating an equal number of interventions to each of the left and right sides through the randomly selected system of sealed envelopes drawn prior to the procedure. Uneven loss to follow-up or withdrawal may cause one intervention-control-side combination to be over-represented.

Modifiers

Age

Increasing age has been associated with increased procedural difficulty. We have excluded individuals 45 years or older to minimise the effect of age.

Peri-operative medications

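### Swelling is analysed as change from baseline without the side's own baseline as a covariate: a valid analysis that gives up some precision, by an amount the protocol does not allow one to fix

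*Protocol*

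**What the plan says.** Swelling is listed among the primary objectives. In the Protocol, Measurement of facial swelling, three tape lines are averaged for each side, and "facial swelling (%) will be calculated as: [(postoperative measurement – preoperative measurement] × 100". The bracket is unbalanced and nothing is divided by, although the result is called a percentage.

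Baseline data exist for each side. Data collection, item 4, says that before surgery patients will "Have a triplicate of baseline measurements to later aid in assessing facial swelling will be recorded", and the Appendix 1 form has separate right and left tables.

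Statistical approach specifies mixed-model ANOVA with "suture type as a within-subjects variable and age, sex, ethnicity, smoking status, previous pericoronitis and dental anxiety score as between-subjects variables". It adds: "In the case of inflammation, irritation and pain, we will use a repeated measures design to account for multiple follow-ups". No pre-operative facial measurement, of the side or of the patient, is in that list. Two other remarks do not supply one. The comparison with baseline mentioned under Post-operative diary follows the VAS text, and the Confounders paragraph names no variable.

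**The concern.** In a split-mouth trial the suture effect is estimated from differences between the two sides of the same mouth. The six listed covariates are constant within a patient, so as main effects they cannot reduce the error of that contrast. For swelling, the side's own pre-operative measurement is a collected variable that could.

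The plan uses that measurement only by subtracting it. The left-right difference before surgery mixes true facial asymmetry, which persists, with random tape error, which does not. Only the first part predicts the post-operative difference, so the best coefficient is below 1 whenever there is random tape error. Fixing it at 1 adds noise. What is at stake is the width of the interval for swelling, tested at alpha 0.01; validity is not in question.

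**Working it through.** **The plan's own figure.** Paired t-test, alpha 0.01 (two-sided), d = 0.5, n = 63: power from the noncentral t is 0.901, so 63 reproduces. 63/0.90 = 70, the recruitment target. The effect size is justified by closure time, which has no baseline, so these figures are unaffected by this point.

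**Set-up.** For each patient let D be the knotless side minus the control side.

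- D_pre = asymmetry + tape error; variance a + e
- D_post = asymmetry + swelling difference + tape error; variance a + s + e
- Covariance of the two = a

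The components are taken as independent, and e is the error variance of the side difference at one visit. The protocol gives no value for a, e or s, so everything below is assumed.

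**Change score.** Var(D_post − D_pre) = s + 2e.

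**Baseline-adjusted.** The slope on D_pre is a/(a+e). The residual variance is a + s + e − a²/(a+e) = s + e + ae/(a+e).

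**Excess.** (s + 2e) − [s + e + ae/(a+e)] = e²/(a+e).

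**Saving.** [e²/(a+e)]/(s+2e).

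Results with e = 1. The last two columns are simulated power at n = 63, two-sided alpha 0.01, 8,000 trials per row, with the effect set so that the adjusted contrast has d = 0.5:

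| a | s | slope | change variance | adjusted variance | saving | power, change | power, adjusted |
|---|---|---|---|---|---|---|---|
| 9 | 9 | 0.90 | 11 | 10.9 | 0.1/11 = 0.9% | 89.5% | 89.3% |
| 3 | 3 | 0.75 | 5 | 4.75 | 0.25/5 = 5% | 88.3% | 89.6% |
| 1 | 1 | 0.50 | 3 | 2.5 | 0.5/3 = 17% | 83.1% | 89.9% |
| 0 | 1 | 0 | 3 | 2 | 1/3 = 33% | 72.3% | 89.8% |

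The extreme a = s = 0 gives 1/2 = 50%. In the first row the two analyses cannot be told apart.

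**Effect of the triplicate.** Suppose a single reading had a = e = s, and the three readings are averaged with independent errors. Then e falls to a third, so a = s = 3e, and the saving drops from 17% to 5%. The excess e²/(a+e) falls faster than e itself.

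**Percent change.** If a denominator was intended, the numerator is still post minus pre. Dividing by the baseline does not remove its error, so correcting the formula does not settle this point.

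**The case against.** The case against is strong on size. The protocol offers no evidence of random tape error. Its one remark, in Post-operative outcome assessment, is "A limitation of this method is soft tissue compression during measurement, which would lead to systematic error", and a constant offset cancels in a change score. Triplicate readings and the mean of three lines already limit random error. The change score follows a cited split-mouth study, is unbiased under randomised sides, and covariate detail may be added in an analysis plan that is not shown. Statistical approach also speaks of inflammation, so reading it as the tape measurement is an inference, although no other inflammation measure is defined. All of this stands, and it makes the point low priority. It does not remove it, because the protocol does write down both the outcome formula and a covariate list, and the list omits a variable that is collected.

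A reader might also infer a larger loss from the shortcut by which adjusted variance is (1+r)/2 of change-score variance, with r the correlation of D_pre and D_post. That shortcut needs equal variances before and after surgery, which here means s = 0: no variation between patients in side-to-side swelling. This is implausible at 48 h. With a = e = s, r = 1/√(2×3) = 0.41 and the shortcut gives a 30% saving; the true figure is 17%. With a = s = 3e, r = 3/√(4×7) = 0.57 and it gives 22%; the true figure is 5%. A low r can come from real swelling variation, in which case the change score loses almost nothing.

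**Conclusion.** The point holds as a missed gain in precision of unknown size. With independent components and any random tape error, the change score carries excess variance e²/(a+e). The variance saved by adjustment runs from under 1% through 5% and 17% under the assumed settings, and is larger only when tape error dominates asymmetry and swelling variation. Triplicate readings, if averaged, make the low end more likely.

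Three stronger readings are not supported. The analysis is not biased, because the side is randomised and subtracting the same side's baseline already removes true asymmetry. The sample size is not wrong, because 63 reproduces and rests on closure time; no power is claimed for swelling. A material power loss cannot be asserted either, because the protocol gives no standard deviation, reliability or correlation for the tape measurements.

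**What to change.** In Measurement of facial swelling and Statistical approach, state that the swelling model at 48 h and 7 days includes the same side's pre-operative measurement, averaged over the triplicate, as a side-level covariate, with the patient's mean baseline as a separate term so that the within-patient slope is estimated on its own. The outcome may be the post-operative measurement or the change in mm: with that covariate in the model both give the same suture estimate. Percentage swelling may still be reported, once its formula is completed. Say also that inflammation in the model means this measurement.

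The cost is about one degree of freedom per slope and a few words of analysis text. No new data, visits or patients are needed.

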Local anaesthetic (lignocaine 2% with adrenaline 1:100 000) will be administered via an inferior dental block and buccal infiltration to the procedural sites prior to incision.

A two-sided flap design will be used, where the:

- 1. papilla distal to the first molar will be incised but not relieved,
- 2. the papilla distal to the second molar will be incised and relieved,
- 3. with a distal relieving incision across the external oblique ridge
 - a. In the event further exposure is required, an additional mesial relieving incision incorporating the distal papilla of the second molar will be made, making the flap 3-sided.

b. This will be determined pre-operatively, and where deviation from the planned flap design has occurred, this will be recorded.

The impacted third molar will be removed following any required sectioning of the tooth and bone removal.

The procedural site will be closed with simple interrupted 3-0 vicryl rapide sutures on the control side and the intervention side will be closed with a continuous running 3-0 v-loc suture. The difference in closure pattern is due to the differences in material handling and application.

A prescription for post-operative pain relief including 1g paracetamol, 400mg ibuprofen orally 4 times daily as needed, will be provided. Additional rescue analgesia will be prescribed, consisting of either 30mg codeine phosphate or 50mg of tramadol orally 4 times a day as needed. If required, the rescue analgesia will be recorded as part of the patient's post-operative pain diary. Patients who are unable to tolerate these medications will be excluded from this study.

Patients who require additional monitoring will be reviewed as per the institution's policy around post-operative complications.

Post-operative diary

The participants will be asked to rate the pain intensity as well as irritation from the sutures for the first 48 hours, every 6 hours while awake. A non-graduated visual analogue scale (VAS) will be provided to the patients for recording of this information as part of their pain diary.

The VAS will comprise of two 100mm horizontal lines with no markings along its length. The left end will be anchored with a vertical line and labelled 'no pain' and the right similarly anchored with a vertical line and labelled 'worst pain imaginable'. The score is determined by the distance between the end of the line on the left and the participant's mark.

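### The analysis model has no term for left or right side, the one factor the allocation balances; adding it costs one degree of freedom

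*Protocol*

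**What the plan says.** Under Statistical approach, each outcome is to be analysed by its own mixed-model ANOVA, with "suture type as a within-subjects variable and age, sex, ethnicity, smoking status, previous pericoronitis and dental anxiety score as between-subjects variables". Outcomes with several follow-ups get a repeated-measures version. Side does not appear in the model.

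Side is treated as a design matter. Randomisation provides equal numbers of sealed allocations to each site. The Bias paragraph says: "Handedness will be controlled for by allocating an equal number of interventions to each of the left and right sides". It then adds: "Uneven loss to follow-up or withdrawal may cause one intervention-control-side combination to be over-represented". No analytic response follows there. The Confounders paragraph promises in general terms that confounding will be dealt with by modelling, but does not name side.

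The intervention side is among the items listed under Data entry, so the variable will be available. Two other side-level facts are collected. For the flap (Surgical procedure), "where deviation from the planned flap design has occurred, this will be recorded"; and in Data collection, item 5, "The time taken for removal of the mandibular third molar from each side will be recorded".

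**The concern.** In a split-mouth trial the suture effect is estimated from the difference between the two sides of one mouth. Age, sex, ethnicity, smoking, pericoronitis history and dental anxiety are the same on both sides, so as main effects they drop out of that difference. Left or right side does not drop out. If one side is systematically slower to close or more painful, each paired difference moves up or down according to which side received the knotless suture. A single operator treats every patient, so such a shift would not average out across surgeons.

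Two things are at stake. With balanced sides, the shift inflates the estimated error without making the estimate any less precise, so the test is conservative. With unbalanced sides, part of the shift enters the suture estimate. The protocol names this second risk, but its model contains nothing that addresses it.

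**Working it through.** **Inputs.** From Sample size: "paired sample t-test analysis with alpha of 0.01, power of 0.9, and a moderate effect size (Cohen's d = 0.5"), 63 evaluable and 70 recruited, so 7 losses are allowed for. From Randomisation: equal allocation, hence 35/35 if all 70 allocations are used. Assumption: the left-right effect *s*, in SDs of the paired difference, is not given in the protocol, so a range is shown. The calculation uses one difference per patient, as the protocol's own power analysis does.

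**1. The stated sample size.** An exact paired t-test (noncentral t, two-sided alpha 0.01, d = 0.5) first reaches 90% power at n = 63 (power 0.9007). The stated 63 is reproduced, and 63/0.90 = 70.

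**2. The six patient-level variables.** In a simulated set of 63 pairs, the suture estimate was 0.3318 with SE 0.1129 both with and without the six main effects, and the same from a paired t-test. If the variables were crossed with suture, using 6 to 12 degrees of freedom, power at n = 63 would move from 0.901 to between 0.899 and 0.896. They neither help nor materially hurt.

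**3. Side.** Write each paired difference as D = τ + s·v + e, with v = +1 or −1 according to the side given the intervention. When sides are balanced:
- the mean of D has sampling variance σ²/n, because balance cancels s;
- a model without side estimates that variance as about (σ² + s²)/n, which is too large.

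The power consequence depends on what d = 0.5 is scaled by, which the protocol does not say. Simulated power at n = 63, 32/31 split, 40,000 replicates:

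| Reading of d = 0.5 | s | Side omitted | Side modelled |
|---|---|---|---|
| SD of observed differences (σ² + s² = 1) | 0.25 | about 91% | not needed for the point |
| same | 0.5 | about 94% | about 97% |
| Residual SD after side (σ = 1) | 0.25 | about 89% | 90% |
| same | 0.5 | about 85% | 90% |

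On the first reading at s = 0.5, σ = √0.75 = 0.866, so the effect in residual units is 0.5/0.866 = 0.577. That is where the 97% comes from. On the second reading at s = 0.5, the type I error without side is about 0.4% against a nominal 1%. The error is conservative, not inflated. With s = 0 there is nothing to gain, and modelling side costs almost nothing: 0.9007 becomes 0.9004 when balanced, and about 0.896 at a 35/28 split.

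**4. Unbalanced loss.** Without side in the model, the bias is s·(n₁ − n₂)/n. The worst case with 7 losses is 35/28, giving 7/63 = 0.111 times s, which is 0.056 SD at s = 0.5. The sign depends on which group loses patients. If loss is unrelated to side, the expected bias is zero, the mean imbalance is about 2 patients, and the chance that all 7 come from one group (either one) is 2·C(35,7)/C(70,7), about 1.1%. With side modelled, the bias is zero at any split.

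**The case against.** The strongest reply is that the planned power is not at risk. The sample size is "based on a paired sample t-test analysis with alpha of 0.01", and that test has no side term. The natural reading is that d is scaled by the SD of the observed differences, which already contains any left-right variation. On that reading the balanced design without side still exceeds 90%. This stands: a reader might infer that the stated power is not delivered, and the protocol does not support that. Only the less natural residual reading brings balanced power below 90%.

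A reader might also infer that the six covariates waste power. They do not, as step 2 shows. They may even have a purpose, since the Modifiers section discusses age, smoking and pericoronitis. Crossed with suture, they would examine effect modification, although the text does not say whether interactions are meant.

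A further inference would be that dropout will bias the results. That needs both a side effect and side-related or unlucky loss. It hardly touches closure time, the protocol's key outcome, which is measured during surgery. Nor does the protocol say that a left-right difference is expected; it says only that handedness will be controlled.

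Finally, the general confounder statement, or a statistical analysis plan not shown here, might bring side in. That is possible, but the protocol sets out a specific list of variables, names a side-related threat, and leaves side off the list.

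**Conclusion.** The point holds as a low-cost improvement. The analysis should include the factor that the allocation balances, and as written it does not. If no left-right effect exists, nothing is lost by the omission. If one exists, the test is conservative and gives up power: about 3 percentage points at s = 0.5 when d is scaled by the observed differences (94% against 97%), or about 5 points when it is scaled by the residual (85% against 90%). The bias from unbalanced loss is at most 0.111 times the side effect under the protocol's own loss allowance. It is zero in expectation if loss is unrelated to side, and it concerns mainly pain, irritation and swelling. All these sizes rest on an assumed *s*, for which the protocol gives no figure. The sample size of 63 is correct for its stated inputs and is not in question.

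It is tempting to say that flap type and tooth-removal time should also be in the model because they differ between sides. The protocol does not support that for the primary analysis. Data collection, item 5 has the side drawn before the procedure, so removal time and any change of flap may come after allocation is known and could be influenced by it.

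**What to change.** In Statistical approach, add left/right side as a fixed within-patient factor in the models for closure time, pain, irritation and swelling. State that the suture effect is estimated with side in the model, whether or not the final numbers are balanced. The Bias paragraph can then cite this as the response to uneven loss.

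State whether the six patient-level variables enter as main effects only or are crossed with suture. Label any suture-by-patient-variable terms as exploratory effect modification, separate from the main suture comparison. Do not add flap type or tooth-removal time to the primary model.

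The cost is one degree of freedom and a few sentences. The intervention side is already to be entered in the data set, and neither the sample size nor the conduct of the trial changes.

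### The awake-only pain and irritation diary yields incomplete or irregularly timed ratings, and the planned repeated-measures ANOVA with polynomial contrasts does not fit them as worded

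*Protocol*

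**What the plan says.** Primary objectives lists closure time, pain, swelling and tissue irritation. Under Post-operative diary, patients rate pain and irritation "for the first 48 hours, every 6 hours while awake". Data collection, item 6, asks for this on each side, with a VAS that "will be included, for every waking 6 hour interval". The same item lists what else the diary records: the interval from the end of the procedure (whose time is written in the booklet) to first rescue medication, the amount of rescue analgesia, and adverse events. A clock time for each rating is not listed.

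Statistical approach plans separate mixed-models ANOVAs in R, with suture type within subjects and patient characteristics between subjects. It continues: "In the case of inflammation, irritation and pain, we will use a repeated measures design to account for multiple follow-ups". Then: "A post-hoc polynomial comparison of follow-up outcomes by suture type will also be used", to see whether healing trajectories differ. It does not define the time levels, say whether the diary ratings are among the follow-ups, or say how sleeping intervals enter the model.

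Swelling is measured before surgery, at 48 h and at 7 days (Measurement of facial swelling). I take this to be what the analysis text calls inflammation.

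**The concern.** A classical repeated-measures ANOVA needs the same filled time cells for every patient, and a polynomial trend needs those cells to mean the same elapsed time. A diary kept only while awake does not supply both. Which ratings are absent depends on when surgery ended and when the patient slept.

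At stake are the number of patients analysed, the precision, and the meaning of the trajectory test for pain and irritation. One part cannot be left to a later analysis document: if rating times are not written down, they cannot be recovered.

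**Working it through.** **1. The plan's own figure.** Sample size states "Power analysis yielded a sample size of 63 participants", with "alpha of 0.01, power of 0.9" and a paired standardised difference of 0.5. The normal approximation is ((2.576 + 1.282)/0.5)² = 59.5, so 60. The exact noncentral-t calculation, two-sided, gives power 0.895 at n = 62 and 0.901 at n = 63. The figure of 63 reproduces. It rests on closure time, which is measured once per side and does not involve the diary.

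**2. Fixed 6-hourly grid.** Nominal ratings fall at 6, 12, …, 48 h, which is 8 per side. Slots are 6 h apart, so any sleep of at least 6 h covers at least one slot. Two such nights therefore empty at least 2 of 8. The protocol gives no sleep or surgery times, so these are assumptions: surgery ends 09:30–17:00, bedtime is 21:30–00:30 (both uniform), and sleep lasts 4 to 9 h on both nights. Simulation gives:

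| Sleep (h) | Mean slots missed of 8 | Patients with all 8 |
|---|---|---|
| 4 | 1.2 | 39% |
| 5 | 1.6 | 20% |
| 5.5 | 1.8 | 10% |
| 6 | 2.0 | 0% |
| 7 | 2.4 | 0% |
| 8 | 2.6 | 0% |
| 9 | 2.9 | 0% |

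With 63 patients and 8 h of sleep, a complete-cell analysis of all 8 slots keeps 0 patients. A linear mixed model fitted to the same kind of data (40 simulated trials, true suture difference −5) keeps all 63, uses about 700 of the 63 × 2 × 8 = 1008 nominal ratings, and gives a mean estimate of −4.9 (simulation standard error 0.2).

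**3. Slots counted by waking interval.** Take sleep from 23:00 to 07:00.

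- Surgery ends 10:00: the 18 h and 42 h slots fall at 04:00, so ratings come at 6, 12, 24, 30, 36 and 48 h.
- Surgery ends 16:00: the 12 h and 36 h slots fall at 04:00, so ratings come at 6, 18, 24, 30, 42 and 48 h.

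Both patients give six ratings and have no empty cells. But the second rating is at 12 h against 18 h, and the fifth at 36 h against 42 h. A polynomial over rating number mixes these times.

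**4. Spacing of the swelling visits.** For days 0, 2 and 7 the mean is 3, the deviations are −3, −1 and 4, and their length is √26 = 5.10. The linear contrast is (−0.59, −0.20, 0.78). Equally spaced scores give (−0.71, 0, 0.71). The separate linear and quadratic components therefore depend on the spacing. The joint two-degree-of-freedom test does not, because with three times both sets span the same space. Appendix 3 labels the last measurement 14 days while the text says 7; these must be reconciled before scores are fixed.

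**The case against.** The strongest objection is that deletion is nowhere stated. The protocol speaks of mixed models in R, which may mean a linear mixed model with ANOVA tests; that keeps every patient, and the remedy would then be largely the stated method. This stands as a limit. The within/between-subjects vocabulary leans towards the classical design but does not settle it.

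Second, the follow-ups may be the 48 h and 7 day reviews, where pain and irritation are also asked and sleep leaves no gaps. Exclusion criterion 14 uses the term for appointments, and the section on alveolar osteitis says the main collection points avoid days 3 to 5. This reading is possible. But the diary VAS is to be compared with baseline for analysis, so on this reading the diary has no stated model.

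Third, no eight-slot clock grid is stated, so it does not follow that every patient has empty cells. That is correct; step 3 of the working shows the difficulty that remains without such a grid.

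Fourth, equal spacing is never stated, and R accepts actual times as scores. Also correct: the text is silent on spacing rather than wrong.

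Fifth, time levels and missing intervals are often left to an analysis plan, which is not at hand. That is fair for the model details. It does not cover the diary form, which must capture rating times from the first patient.

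**Conclusion.** The diary is incomplete or irregularly timed by design, and the analysis as worded does not accommodate this on either way of counting slots. On a fixed grid, with at least 6 h of sleep on both nights, at least 2 of 8 slots per side are empty, and a complete-cell analysis would keep none of these patients. On waking intervals, elapsed times for the same rating number differ by 6 h in the example. Sleep length, bedtime and end of surgery are assumptions; below 6 h of sleep some complete rows survive.

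A reader might infer that the plan will discard all patients for pain and irritation, or that the suture comparison will be biased. The documents support neither. Complete-cell analysis is not stated. The same patient rates both sides, so sleep gaps fall on both sutures together and do not by themselves bias the contrast. What is at risk is patients, precision and a meaningful trajectory comparison. Closure time, the sample size of 63 and the collection of swelling data are unaffected by sleep.

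**What to change.** - State that diary pain and irritation will be analysed with a linear mixed-effects model on all available ratings. Fixed effects: suture, side, time, suture-by-time and side-specific baseline. Random effects: patient, and side within patient.
- Define time as actual hours since the end of the procedure, which is already written in the booklet, and add a clock-time box to each diary entry.
- Confirm that the pre-operative VAS is taken for each side; Data collection, item 4, does not say so.
- Say which ratings (diary, 48 h and 7 day reviews) enter which model.
- Base any polynomial contrasts on actual times, including those for swelling at baseline, 48 h and 7 days.

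The cost is analysis wording and one extra field per diary page, to be settled before diaries are printed. No change to the sample size follows.
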